10. INVESTIGATIONAL PLAN

10.1. Study Design

This open-label extension study will be performed at multiple centers currently participating in the double-blind, placebo-controlled, parent trial (EN3835-201) in the United States. The open-label extension study will enroll up to 350 subjects. The study is planned to end when at least 100 subjects have 12 months after exposure ie 12 months after first treatment in study EN3835-201 or study EN3835-202. Subjects who completed the entire double-blind study and sign an informed consent will be eligible to enter this open-label extension.

After the Sponsor has broken the EN3835-201 study drug blind, subjects enrolled in the open-label study will have the following options:

- To have no EN3835 treatments in study EN3835-202
- If received EN3835 in study EN3835-201, may elect to have a qualifying quadrant other than the one treated in study EN3835-201 treated with EN3835 (termed *re-dosing*)
- If received EN3835 in study EN3835-201 and the cellulite severity scores of the treated quadrant have returned to or are greater than EN3835-201 baseline scores, may elect to have the previously treated quadrant retreated with EN3835 (termed *re-treatment*)
- If received placebo in study EN3835-201, may elect to have a qualifying quadrant treated with EN3835; also may elect to have a second qualifying quadrant treated with EN3835 after completing the treatment course

Subjects enrolled in study EN3835-202 who elect to receive EN3835 treatment (either re-treatment, re-dosing, or a first treatment) must meet specific inclusion and exclusion criteria for eligibility during re-screening (Screening B) prior to EN3835 dosing.

Following completion of safety and cellulite assessments at Day 71 of the double-blind study (EN3835-201), subjects will be asked if they wish to continue in the open-label extension to the double-blind study (Screening A). At the time of entry into the open-label study, subjects and Investigators will remain blinded to study drug. Until the EN3835-201 study drug blind is broken by the Sponsor, subjects will undergo observation-only visits at 3-month intervals \pm 7 days (relative to the initial dose in the double-blind study) where both safety and cellulite severity assessments of the treated quadrant will be made.

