Following the study drug blind being broken and communicated to centers, eligible subjects may elect to receive EN3835 treatment. Subjects electing not to receive further EN3835 treatments (observation-only subjects) will continue to be followed for safety and cellulite severity assessments at 3-month intervals through month 12. Up to 14 days prior to initiating treatment injections of EN3835 on open-label treatment visit Day 1, subjects will undergo a screening evaluation (Screening B) to determine if they meet specified inclusion and exclusion criteria and to determine the quadrants, if any, that qualify for treatment.

During Screening B, photographs will be taken of each of the subject's 4 quadrants (left buttock, right buttock, left posterolateral thigh, and right posterolateral thigh). Subjects will again receive instructions for use of the PR-PCSS and will subsequently use the scale to rate the severity of their cellulite in each of the 4 quadrants by comparing digital images of each of their quadrants displayed on standardized computer monitors with the PR-PCSS instrument. This independent self-assessment will take place in a private setting to minimize any potential bias from site personnel. The Investigator will then assess the subject's 4 quadrants live in real-time using the CR-PCSS. The Investigator will rate the 4 quadrants using the Hexsel CSS as described in section 13.1.1.6.(12) Subjects must have at least 1 quadrant that meets the following criteria for inclusion into the treatment phase of the study:

1. PR-PCSS score of 3 or 4, and
2. CR-PCSS score of 3 or 4, and
3. Hexsel CSS score of no greater than 13.

After the independent assessments are completed separately by the subject and the Investigator, the Investigator will review his/her assessments and the subject's assessment to determine which quadrants, if any, are eligible. The eligible quadrant chosen to receive treatment in the open-label study EN3835-202 will be at the discretion of the subject. A quadrant may be chosen for re-treatment if it was the quadrant treated in study EN3835-201 or a new quadrant may be chosen for re-dosing. **NOTE: For subjects who received active drug in the assigned quadrant in the double-blind study, the quadrant must have cellulite severity at (or greater) than the EN3835-201 baseline scores of PR-PCSS and CR-PCSS to qualify for re-treatment.**

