After the independent assessments are completed separately by the subject and the Investigator, the Investigator will review his/her assessments and the subject's assessment to determine which quadrants, if any, are eligible. The eligible quadrants (must meet all 3 of the inclusion criteria (PR-PCSS, CR-PCSS, and Hexsel CSS scores), if any, for treatment will be determined by the Investigator after which the quadrant selected will be at the discretion of the subject. For subjects treated with EN3835 in the double-blind study, if the quadrant treated in the double-blind study (EN3835-201) has PR-PCSS and CR-PCSS ratings identical or more severe than the double-blind study (EN3835-201) PR-PCSS and CR-PCSS baseline ratings (Baseline is Day 1 of study EN3835-201), subjects can elect to have that same quadrant re-treated. Subjects who choose re-treatment of the previously treated quadrant will be classified in the re-treatment arm. If another quadrant besides the previously treated quadrant meets all 3 of the inclusion criteria, subjects can choose to be treated in the naive quadrant. Subjects who choose treatment into a naive quadrant will be classified in the re-dosing arm.

Assessments made with the PR-PCSS (from digital image), the CR-PCSS (live assessment), and the Hexsel CSS score during the open-label Screening B visit will be the baseline severity of EFP in the selected quadrant.

A subject who received placebo in the double-blind study may be treated in the same quadrant in the open-label study if the quadrant still meets all 3 criteria OR another qualifying quadrant may be selected for treatment by the subject. Following Day 71 of a treatment course (3 treatment sessions), subjects can choose to receive a second treatment session in either the same quadrant if it still meets qualification criteria or in a different quadrant that meets qualification criteria. For the first treatment course, these subjects will be considered in the treatment arm. For the second treatment course, if the same quadrant is treated, subjects will be in the re-treatment arm; if a different quadrant is treated, subjects will be considered in the re-dosing arm.

If no quadrant meets all 3 criteria, the subject may continue in the observation-only study with safety and cellulite severity evaluations performed at 3-month intervals but may not receive treatment in this study.

Selecting and Marking Dimples

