• Hexsel Cellulite Severity Scale (CSS)	X ^{h,i}				X ^h	
• Investigator Global Aesthetic Improvement (I-GAIS)					X ^h	
Confirm Eligibility	X	X ^e				
Select Quadrant	X ^j					
Study drug administration		X	X	X		
Injection site reactions/local tolerability in selected quadrant		X	X	X	X	
Adverse events			Monitored Throughout Study			

^a After the study drug blind is broken in study EN3835-201, eligible subjects may elect to receive EN3835 treatments.

^b Upon completion of treatment, subject will be followed at 3-month intervals as in [Table 2](#); if study terminates early, subject will be followed through Visit 4 (Day 71). If subject received placebo in the double-blind study (EN3835-201), she may be eligible for a total of 2 courses of treatment (a total of 6 treatment sessions) in this study.

^c All 4 quadrants are photographed at screening; at other visits, the selected quadrant only is photographed.

^d Before and after marking the dimples.

^e Before injection.

^f Up to 4 hours before injection; approximately 15 and 30 minutes after injection. Vital signs must be stable before the subject is discharged.

^g Assessment made via photograph (if treatment session, use photograph taken before marking dimples).

^h All 4 quadrants are assessed at the Screening B visit; at other visits, the selected quadrant only is assessed.

ⁱ Initial Hexsel CSS at screening must be ≤ 13 on selected quadrant.

^j To qualify for treatment, the selected quadrant must have a score of 3 or 4 (moderate or severe) in both the CR-PCSS and PR-PCSS, and a Hexsel CSS score ≤ 13 ; to qualify a quadrant that had been previously treated with EN3835 in study EN3835-201, the quadrant must have CR-PCSS and PR-PCSS scores equal to or greater than study EN3835-201 baseline scores and a Hexsel CSS score ≤ 13 .

^k Medical history and prior medications will be based on EN3835-201 eCRF; only updates and concomitant medications need to be captured at Screening B visit.

^l Do not conduct if Screening B visit date is within 12 months of obtaining an ECG during the double-blind study (EN3835-201).

^m Do not conduct on subjects eligible and opting-in for a second course of treatment in the current study (EN3835-202) if Screening B visit or Day 1 visit for second treatment course is the same day as Day 71 of the first treatment course in this study or previous study EN3835-201.

ECG=Electrocardiogram; eCRF=Electronic case report form; EFP=Edematous fibrosclerotic panniculopathy; Tx=Treatment

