2. ANALYSIS POPULATIONS AND PHASES

The following populations will be considered in the statistical analysis of the study:

- Observation Population: The Observation population includes all subjects rolled over from study EN3835-201. The cellulite assessment evaluations and safety analyses on data collected during observation phase will be performed using this population.
- Safety Population: The Safety population will include all subjects who receive at least 1 dose of EN3835 in the current study. All safety analyses for the treatment phase will be performed using this population. For by region summaries, safety population is considered within each treatment course.
- Effectiveness Population: The Effectiveness population includes all safety subjects who have a baseline and at least 1 post-baseline assessment on both the CR-PCSS and PR-PCSS on the quadrant selected for treatment in the current study. All analysis of effectiveness for the treatment phase will be based on this population. For by region summaries, effectiveness population is considered within each treatment course.
- Durability Population: This population is defined as all active responders who have both CR-PCSS and PR-PCSS at 180 days or above. The active responders are subjects treated with EN3835 with improvements of at least 1 level on each

scale (CR-PCSS and PR-PCSS) at Day 71 visit compared to the baseline. Analysis of durability of treatment effect will be performed using this population.

- Durability Population for Double-blind Treated Subjects: This population is defined as all subjects in the durability population who showed an improvement of at least 1 level on each scale (CR-PCSS and PR-PCSS) at Day 71 visit compared to the baseline for the quadrant treated with EN3835 in double-blind study EN3835-201.
- Durability Population for Open-label Treated Subjects: This population is defined as all subjects in the durability population who showed an improvement of at least 1 level on each scale (CR-PCSS and PR-PCSS) at Day 71 visit compared to the baseline for the quadrant treated with EN3835 in the open-label study EN3835-202 study, who did not have the same quadrant treated with EN3835 in double-blind study EN3835-201. For by region summaries, this population is considered within each treatment course.

The following 2 phases will be summarized in the statistical analysis of the study:

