- Observation phase: Observation phase is defined as the time period from Screening A to the first treatment date of the same quadrant in study EN3835-202 or the end of study EN3835-202 if there is no treatment received for the same quadrant in study EN3835-202. Observation phase is defined within each treated quadrant, unless the summary is for subject level only and cannot be differentiated by the treated quadrant, ie, disposition, adverse event (AE). For subject level summaries, observation phase is defined as the time period from Screening A to the first treatment date in study EN3835-202 or the end of study EN3835-202 if there is no treatment received in study EN3835-202.
- Treatment phase: Treatment phase is defined as the time period from the first treatment date of certain quadrant in study EN3835-202 to the end of study EN3835-202. Treatment phase is defined within each treated quadrant, unless the summary is for subject level only and cannot be differentiated by the treated quadrant, ie, disposition, AE. For subject level summaries, treatment phase is defined as the time period from the first treatment date to the end of study EN3835-202.

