6.2.3. Observation Endpoints

Observational endpoints for treated quadrant in study EN3835-201 include:

- Change from baseline for PR-PCSS
- Proportions of composite responders defined as subjects with an improvement in severity from baseline of at least 2 (or 1) levels of severity in the CR-PCSS and an improvement in severity from baseline of at least 2 (or 1) levels of severity in the PR-PCSS

- Proportion at each level of improvement in the PR-PCSS:
 - Proportion of patient responders defined as subjects with an improvement in severity from baseline of at least 2 levels on the PR-PCSS
 - Proportion of patient responders defined as subjects with an improvement in severity from baseline of at least 1 level on the PR-PCSS
- Change from baseline for CR-PCSS
- Proportion at each level of improvement in the CR-PCSS:
 - Proportion of Investigator responders defined as subjects with an improvement in severity from baseline of at least 2 levels on the CR-PCSS (Investigator rated)
 - Proportion of Investigator responders defined as subjects with an improvement in severity from baseline of at least 1 level on the CR-PCSS (Investigator rated)
- Proportion of responders at each level of the subject satisfaction at Day 360
- Hexsel CSS total score changed from the study EN3835-201 baseline at Day 71 of study EN3835-201 and Day 360 or Day 360 Beyond long-term durability visits.

These endpoints will be summarized by treatment groups assigned in study EN3835-201 and treated region (buttock or thigh) and overall and by study day using appropriate descriptive statistics.

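### The by-arm observation tables in SAP 6.2.3 do not separate ratings made before and after the 201 blind was broken, so later arm differences cannot be read as an EN3835 effect

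*Combined protocol and SAP*

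**What the plan says.** SAP 6.2.3 lists CR-PCSS and PR-PCSS changes and responder proportions, Hexsel change and subject satisfaction for the quadrant treated in 201. It then says: "These endpoints will be summarized by treatment groups assigned in study EN3835-201 and treated region (buttock or thigh) and overall and by study day".

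The population is defined in SAP section 2: "The Observation population includes all subjects rolled over from study EN3835-201". Women given placebo in 201 are therefore included. This is a SAP change, recorded in SAP section 9; Protocol 17.2.1 confined its Observational population to women given EN3835 in 201 and not treated in EN3835-202 (202).

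SAP section 2 also sets when a quadrant stops contributing: "Observation phase is defined as the time period from Screening A to the first treatment date of the same quadrant in study EN3835-202". A quadrant never treated in 202 contributes until that study closes.

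On blinding, Protocol 10.1 says: "At the time of entry into the open-label study, subjects and Investigators will remain blinded to study drug". It continues: "Following the study drug blind being broken and communicated to centers, eligible subjects may elect to receive EN3835 treatment". Observation visits carry on alongside treatment (SAP 1.2).

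Eligibility for open-label treatment depends on the 201 arm. For placebo, Protocol 12.1.4 says: "A subject who received placebo in the double-blind study may be treated in the same quadrant in the open-label study if the quadrant still meets". The criteria meant there are PR-PCSS 3 or 4, CR-PCSS 3 or 4, and Hexsel no greater than 13. For a quadrant given EN3835 in 201, SAP Table 3, footnote j, says: "the quadrant must have CR-PCSS and PR-PCSS scores equal to or greater than study EN3835-201 baseline scores". The same Hexsel limit applies.

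SAP 8.1 imputes missed CR-PCSS and PR-PCSS visits backward from the next available visit. SAP 3.1 sets the default denominator as the number of subjects in the column.

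**The concern.** PR-PCSS is rated by the woman and CR-PCSS by the investigator. Once the break is communicated, both can know what was injected in 201; the treatment options offered depend on it. Visit timing is counted from Day 1 of 201, while the break happens once in calendar time. A given study-day column can therefore hold blinded ratings from women who enrolled early and unblinded ratings from women who enrolled late, with nothing to tell them apart. Backward imputation adds a second route: the example in SAP 8.1 carries a Day 270 score back to Days 180 and 90, so a score given after the break can fill a visit that was due before it.

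The break also starts treatment in 202, and quadrants then leave the phase depending on their scores. The SAP gives no rule for these exits; SAP 8.1 addresses missed visits only.

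At stake is the one effectiveness summary specified by 201 arm. Ratings before the break are the only blinded, placebo-controlled follow-up in the study, and they are free of exits because open-label treatment had not begun. The plan merges them with ratings that have neither property.

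**Working it through.** **The plan's own figure.** Protocol 17.1 expects 95% of 350 women: 0.95 × 350 = 332.5, rounded up to 333, or about 166 per arm at 1:1. The point does not rest on this. No alpha, power or effect size applies, because the summaries are descriptive.

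**Step 1: where the two eligibility rules disagree.** Scores are written (PR, CR), with Hexsel assumed to be within the limit. A placebo quadrant may be treated if both current scores are at least 3. An active quadrant may be re-treated if both are at or above its own 201 baseline. Baseline scores were 3 or 4 (Protocol, Table 4).

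| 201 baseline | Current scores at which placebo may leave and active may not |
|---|---|
| (3,3) | none |
| (3,4) | (3,3), (4,3) |
| (4,3) | (3,3), (3,4) |
| (4,4) | (3,3), (3,4), (4,3) |

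The disagreement always runs the same way. An active 1-level composite responder can never leave by re-treatment; a placebo responder who went from (4,4) to (3,3) can. At baseline (3,3) the rules coincide, but exit still depends on outcome: quadrants scoring below 3 on either scale stay, and unimproved ones may go.

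**Step 2: what exits alone can do to the 1-level composite.** All inputs here are assumptions, because the documents give none:
- p: true responder share
- b: share with baseline (4,4), the rest (3,3); 0.2 or 0.5
- s = 0.7: share of (4,4) responders now at (3,3)
- m = 0.3: share of (4,4) non-responders down one level on one scale
- k = 0.8: share of (3,3) non-responders still qualifying
- u: share of qualifying quadrants treated

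Shares of each arm still observed:
- Active: R = p; N = (1 − p)[1 − u((1 − b)k + b(1 − m))]
- Placebo: R = p[(1 − b) + b(1 − su)]; N = (1 − p)[1 − u((1 − b)k + b)]

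The rate is R/(R + N) among quadrants still observed, and R over the full column.

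*Example A:* p = 0.4 in both arms, b = 0.5, u = 0.6 in both.
- Active: R = 0.400; N = 0.6 × (1 − 0.6 × 0.75) = 0.330; rate 0.400/0.730 = 54.8%.
- Placebo: R = 0.4 × (0.5 + 0.5 × 0.58) = 0.316; N = 0.6 × (1 − 0.6 × 0.90) = 0.276; rate 0.316/0.592 = 53.4%.
- Apparent difference: +1.4 points among those still observed; 40.0 − 31.6 = +8.4 over the full column.

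*Example B:* p = 0.4 in both arms, b = 0.2, u = 0.2 active and 0.6 placebo.
- Active: N = 0.6 × (1 − 0.2 × 0.78) = 0.506; rate 0.400/0.906 = 44.1%.
- Placebo: R = 0.4 × (0.8 + 0.2 × 0.58) = 0.366; N = 0.6 × (1 − 0.6 × 0.84) = 0.298; rate 0.366/0.664 = 55.2%.
- Apparent difference: −11.1 among those still observed; +3.4 over the full column.

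Ranges of the apparent active-minus-placebo difference, in points:

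| True difference and uptake | Still observed | Full column |
|---|---|---|
| 0 (p = 0.2 or 0.4), equal uptake 0.3 or 0.6 | +0.4 to +1.4 | +0.8 to +8.4 |
| 0 (p = 0.2 or 0.4), uptake 0.2 active, 0.6 placebo | −11.1 to −7.3 | +1.7 to +8.4 |
| +30, all uptake settings | +22.6 to +38.8 | +30.4 to +34.2 |

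**Step 3: the 2-level composite.** Such a responder scores at most 2 on both scales and qualifies under neither rule. Over the full column, exits then change nothing: with 166 placebo women and an assumed 10% rate, 16.6/166 = 10%. Among quadrants still observed, if 90% of non-responders qualify and 60% of those are treated, the rate is 16.6/(16.6 + 149.4 × 0.46) = 16.6/85.3 = 19.5%; at 40% and 80% uptake it is 14.8% and 28.4%.

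Rating bias from unblinding comes on top and cannot be quantified from the documents.

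**The case against.** The best defence is that nothing inferential hangs on these tables. SAP 3.1 makes the results descriptive, the primary objective is safety, the durability objectives name only women given EN3835 in 201, and SAP 6.3 analyses EN3835-treated responders only. A reader might infer that the plan states a long-term controlled comparison and gets it wrong; it states no such comparison. That stands and lowers the priority. It does not remove the point, because columns for randomized arms, side by side by study day, will be read as a comparison. The word uncontrolled in Protocol 8.6 refers to quadrants with moderate or severe cellulite treated with EN3835, not to this table.

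Other stronger readings also go too far:
- That the arms always face different exit rules. They differ only where a 201 baseline score was 4, and the baseline mix is not given.
- That observation ratings are themselves the route to open-label drug. Eligibility rests on separate Screening B ratings.
- That every study day mixes blinded and unblinded ratings. This depends on the date of the break and the enrolment calendar, neither of which is given; early visits may be wholly blinded.
- That the arm comparison runs past Day 360. SAP Table 4, footnote d, restricts those visits to quadrants given EN3835.
- That exits push the result in a known direction. Step 2 shows either sign, and Step 3 shows no exit effect for the 2-level composite under the default denominator.

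A pre-break table also selects earlier enrollees at later study days. That is a fair cost, and a reason to keep the later ratings on display rather than suppress them.

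**Conclusion.** The point holds in limited form. SAP 6.2.3 can pool blinded and unblinded subjective ratings within a study-day column up to Day 360, can import unblinded scores into earlier visits by imputation, and has no rule for score-dependent exits that differ by arm when a 201 baseline score was 4. By-arm differences at the affected visits cannot be read as an EN3835 effect.

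The illustration shows apparent 1-level differences of −11.1 to +8.4 points with no true effect. It rests entirely on assumed response, baseline mix and uptake, and the sign turns on uptake and denominator. The eligibility rules themselves are not in question here, only how the tables handle them. Because the table is descriptive and secondary to safety, this is a cheap improvement rather than a flaw in a stated inference.

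**What to change.** In SAP 6.2.3:
1. Flag each CR-PCSS, PR-PCSS and Hexsel rating as before or after the date the 201 blind was broken and communicated to that site.
2. Build the by-arm table from pre-break ratings only, with the number rated at each study day as denominator. State in SAP 8.1 that no post-break rating is imputed backward into this table.
3. Show post-break ratings in a separate table labelled unblinded. Give the number of quadrants that left for 202 treatment in each arm, and note that arm differences there are not interpretable as a treatment effect.

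The cost is one date flag per site and a split of existing tables, with no new data. Protocol 17.9 already used the break as a cut-off for a safety analysis, although SAP 1.6 plans no interim analysis. The downside is fewer, earlier-enrolled women in the blinded columns at later study days.
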